### 9.3. Vital Signs Including Height and Weight

Summaries for vital signs will be provided using descriptive statistics and the safety population. Vital signs include the following parameters:

- Blood Pressure, Systolic (mmHg)
- Blood Pressure, Diastolic (mmHg)
- Height (cm)
- Weight (kg)
- BMI (kg/m^2)

- Heart Rate (beats/min)
- Respiratory Rate (breaths/min)
- Temperature (C)

Non-blood pressure vital signs (Height, Weight, BMI, Heart Rate, Respiratory Rate, Temperature) will be presented in one summary and blood pressure (Systolic, Diastolic) will be presented in other summaries (one each for systolic and diastolic).

Summaries will present scheduled visit and include baseline (Screening, Baseline, W1D1, W1D2, W1D3, W1 Safety Assessment, W2D1, W2D2, W2D3, W2 Safety Assessment, Limited Safety Assessment, EOT, EOS 1 Week Post-excision, EOS 2 Weeks Post-excision – not all vital signs are collected at all scheduled visits) within the parameters mentioned previously in this section of the SAP and include descriptive statistics for baseline and change from baseline for post-baseline visits, if possible.

Blood pressure is also to be measured and will be displayed by scheduled timepoint (Pre-injection, 1 Minute Post-injection, 3 Minutes Post-injection, and then 5 through 120 Minutes Post-injection in increments of 5 minutes) within injection (Injection 1, Injection 2 – not all timepoints are collected for all injections) within scheduled visit and include descriptive statistics for change from pre-injection for post-injection readings on that same visit, if possible.

A summary will also be provided for the number of events, and the number and percentage of subjects with at least one event, for each of the following parameters within injection visit (W1D1, W1D2, W1D3, W2D1, W2D2, W2D3):

- 20 mmHg decrease in systolic BP with absolute systolic BP < 100 mmHg
- 20 mmHg decrease in systolic BP with clinical symptoms
- Absolute diastolic BP < 60 mmHg

Decrease in systolic BP will be determined three ways: (a) change from baseline, (b) change from pre-injection for post-injection readings on that same visit, and (c) change from the previous most recent non-missing reading on the same visit. The clinical symptoms tabulation related to a decrease in systolic BP will be determined by counting TEAEs with a start date matching the BP event date that are (a) recorded as DLTs (Part 1) or TRAEs SI (Part 2), (b) related to study treatment, and (c) have the following symptomatic events: Dizziness, Shortness of breath, Fainting, Nausea, Diaphoresis, Blurry vision, Headache, Fatigue. For symptomatic events, the PTs that will be used are

as follows: Dizziness, Dyspnoea, Syncope, Nausea, Hyperhidrosis, Vision blurred, Headache, Fatigue.

A separate listing will be provided for Vital Signs using the safety population, and this listing will include Vital Signs Collected (Yes, No), Visit, Date of Reading, Reading Value and Unit, and Change from Baseline for all parameters.

For BP collected on injection days, the listing will include BP Collected After Injection (Yes, No), Visit, Date and Time of Reading, Timepoint of Reading, Injection Number, Reading Value and Unit, Change from Baseline, Change from Pre-injection for post-injection readings on that same visit, if possible, Change from the Previous Most Recent non-missing reading on the same visit, if possible, and Reason Timepoint Not Done.

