## 8.4.2 Vital Signs Data

Height and weight will be obtained at Screening and EOS.

Vital signs (e.g., body temperature, BP, and heart rate [HR]) will be obtained at all visits after the subject has been in the supine position for at least 5-minutes. Vital signs will be measured at the final evaluation during the EOS visit before the subject is discharged from the study.

On VP-315 dosing days, blood pressure will be monitored serially (observing for hypotension that meets the definitions as described in Section 10.1): just prior to injection, at 1-, 3-, and 5-minutes after each injection, and then every 5-minutes until 2 hours after the last injection of the day using a manual or automated cuff system (Table 8-1). For subjects in Part 2 – Cohorts 4 and 5 expansion groups, monitoring of BP has been decreased to 1-hour post treatment (an additional hour may be continued at the discretion of the PI).

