### 4.1. Treatment-related Adverse Events

TRAEs are treatment-emergent adverse events that are related to study treatment.

Adverse events (AEs) considered DLTs (Part 1) or TRAEs SI (Part 2) are defined as follows. AEs considered DLTs or TRAEs SI are captured in EDC.

- Hypotension meeting any of the following definitions:
  - > 20 mmHg decrease in systolic blood pressure (BP) with absolute systolic BP < 100 mmHg, or
  - > 20 mmHg decrease in systolic BP with clinical symptoms, or
  - absolute diastolic BP < 60 mmHg
- Significant elevation of serum tryptase concentration is defined as an increase of  $(1.2 \times \text{baseline value}) + 2$
- Any Grade 2 or higher AE occurring between start of dose administration and the end of the post-dose observation period on any given treatment day
- Any Grade 2 or higher AE considered by the investigator to be related to the investigational product
- Any Grade 2 or higher local reactogenic AE (injection site pain, erythema, induration)
- Any Grade 2 or higher systemic reactogenic AEs (fever, myalgia, headache)

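### SAP 9.3 reports criterion blood-pressure falls only visit by visit, with no row for subjects affected on any dosing day, and its symptomatic row counts symptoms rather than falls

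*SAP*

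**What the plan says.** SAP 9.3 plans a table of blood-pressure falls against the three hypotension criteria that form part of the DLT/TRAE SI definition. It states: "A summary will also be provided for the number of events, and the number and percentage of subjects with at least one event", and sets the level of tabulation: "for each of the following parameters within injection visit (W1D1, W1D2, W1D3, W2D1, W2D2, W2D3". No row across visits is listed. The Overall group in SAP 5.5 pools cohorts, not dosing days.

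The systolic decrease is determined three ways: (a) from baseline, (b) from the same visit's pre-injection value, and (c) as "change from the previous most recent non-missing reading on the same visit". The SAP does not say whether an event is a reading, an episode or a subject-visit. SAP 5.2's general rule for several readings at one visit makes an exception for visits with pre- and post-dose readings, and it gives no episode rule.

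The symptomatic tabulation "will be determined by counting TEAEs with a start date matching the BP event date". Those TEAEs must also be recorded as DLTs or TRAE SIs, be related to treatment, and carry one of eight symptom preferred terms.

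**The concern.** Hypotension is the first-listed DLT/TRAE SI criterion in Protocol 10.2 and SAP 4.1, and blood pressure is read serially on every dosing day. The natural question is what share of subjects on each regimen had a criterion fall at any time. The table does not answer it. Six per-visit counts cannot be added, because one subject may appear in several of them.

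The event column has a second problem. The symptomatic row is labelled as a blood-pressure decrease but is counted in adverse events. In the other rows the unit is left open, so two programmers could follow the text and produce different numbers. If readings were counted, the result would depend on how long a dip lasted and how long the subject was monitored. Monitoring time differs between the initial and expansion groups, which SAP 5.5 displays separately.

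**Working it through.** The plan states no sample-size or expected-event figure for this table, so there is nothing to reproduce. The checks use the SAP's reading schedule, its cohort sizes and dips assumed for illustration.

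**Inputs**
- Readings after an injection: "1 Minute Post-injection, 3 Minutes Post-injection, and then 5 through 120 Minutes Post-injection in increments of 5 minutes" (SAP 9.3).
- Expansion groups: "monitoring of BP has been decreased to 1-hour post treatment" (Protocol 8.4.2), with a further hour at the investigator's discretion.
- Cohort 4: 36 subjects, up to 4 dosing days. Cohort 5: 37 subjects, up to 6 dosing days (SAP 3.6 and 3.7, initial and expansion subjects together). With one treated lesion the days are 2 and 3.
- Assumed: 4 subjects meet a criterion at each visit. In a dip, systolic pressure goes from 125 to 95 and diastolic from 75 to 55 mmHg, and baseline equals the pre-injection value.

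**1. Subjects affected on any dosing day.** With k subjects affected at each of V visits and N subjects in all, k ≤ any-day count ≤ min(N, kV).
- Cohort 5, V = 6: 4 to min(37, 24) = 24, which is 4/37 = 10.8% to 24/37 = 64.9%.
- Cohort 5, V = 3: 4 to 12, which is 10.8% to 32.4%.
- Cohort 4, V = 4: 4 to min(36, 16) = 16, which is 4/36 = 11.1% to 16/36 = 44.4%.
- Cohort 4, V = 2: 4 to 8, which is 11.1% to 22.2%.

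The per-visit rows cannot show where in these ranges the answer lies.

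**2. Symptomatic row.** One fall with dizziness, nausea and sweating recorded as three qualifying TEAEs counts 3. Three falls on one day with a single qualifying TEAE count 1. The number therefore follows symptoms, not falls.

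**3. If each qualifying reading were an event.** The readings after the last injection are 2 (minutes 1 and 3) + 24 (minutes 5 to 120 by 5) = 26 over two hours, and 2 + 12 = 14 over one hour.
- Dip over minutes 1 to 30 (readings at 1, 3, 5, 10, 15, 20, 25, 30): 8 events under (a), (b) and the diastolic criterion; 1 under (c), at onset.
- Dip over minutes 10 to 40: 7 and 1.
- Dip from minute 5 to minute 120: 24 with two hours of monitoring and 12 with one hour; 1 under (c) either way.
- Gradual fall 125, 115, 105, 95, 90, 90, 95, 110, 120: four readings are below 100 and more than 20 below 125, so 4 under (a) and (b). The largest single step down is 10, so 0 under (c).

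In each case the subject is counted once within the visit, or not at all, so repeat counting leaves the per-visit n (%) unchanged.

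**The case against.** The study is descriptive, with no inference planned. The listing in SAP 9.3 shows every injection-day reading with its time and all three changes, so no information is lost. SAP 9.1 gives subjects with at least one DLT or TRAE SI over all days, by SOC and preferred term. SAP 9.4 treats blood-pressure changes that would qualify as DLT/TRAE SI as sparse and leaves the matching Holter timepoints to listings. Protocol 10.2 ends dosing after a DLT/TRAE SI, which if applied strictly would limit recurrence on later days.

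Much of this stands, and it rules out several stronger readings that a reader might infer:
- That the SAP counts one event per reading. It does not say so; the term is undefined.
- That the per-visit percentages are inflated. Repeat readings or symptoms in one subject do not change them.
- That the symptomatic row ignores blood pressure. A TEAE must start on the date of a BP event.
- That no TRAE SI rate is produced. SAP 9.1 produces one.
- That the three methods ought to agree. They use three declared reference points and will differ.
- That the threshold was changed. SAP 9.3 reads "20 mmHg decrease in systolic BP with absolute systolic BP < 100 mmHg" and SAP 4.1 reads "> 20 mmHg decrease in systolic blood pressure (BP) with absolute systolic BP < 100 mmHg", but SAP 14 declares no change, and a symbol at the start of a bullet may have been lost when the PDF was read.

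It does not remove the point. SAP 9.1 rests on events recorded as DLT/TRAE SI, whereas the first and third criteria in SAP 9.3 need neither relatedness nor an AE record. The readings are therefore the check on what was recorded, and a fall that was never recorded would not stop dosing. Protocol 7.3.1 and 7.3.2.2 also have the medical monitor decide on continuation after a TRAE SI. They need reconciling with 10.2, and meanwhile recurrence across days cannot be excluded. A listing makes the summary possible but does not supply it.

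**Conclusion.** The point holds for the table in SAP 9.3. Two defects follow directly from the text: there is no any-visit subject count, and the symptomatic row is counted in TEAEs. The first leaves the cohort-level share wide open. With an assumed 4 subjects per visit and all dosing days used, it could be 10.8% to 64.9% in Cohort 5 and 11.1% to 44.4% in Cohort 4. If affected subjects prove few, or rarely recur, the range narrows.

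The undefined event is a lesser gap. The eightfold count, and the 24 against 12 for the same long dip, arise only if readings are counted and only for the assumed dips. The point concerns how readings are summarised, not how subjects are managed.

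**What to change.** In SAP 9.3:

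1. Add an any-injection-visit row giving the number and % of subjects per cohort for each criterion.
2. Count a symptomatic event as one BP event with at least one listed, date-matched symptom, not one per TEAE. Because matching is by date, add a footnote that all episodes on such a day are treated as symptomatic.
3. For methods (a) and (b) and the diastolic criterion, count one event per unbroken run of qualifying readings. State how a missing reading, a single reading just outside the threshold, and a dip spanning both injections are handled. Keep method (c) as a separate measure of sudden onset, with a note that it is not expected to agree: the gradual fall above still gives 0.
4. Check the source PDF for the missing symbol. Align the systolic rows with SAP 4.1 and Protocol 10.2 only if it is really absent.

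The cost is a few sentences and minor programming on timed data already collected. Event counts will be lower than a count of readings. The change belongs before database lock, since SAP 5.2 labels later additions post hoc.

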#### **9.4.    Electrocardiogram**

Summaries for electrocardiogram (ECG) readings from 12-lead and Holter/telemetry 5-lead assessments will be provided using the safety population. A continuous summary and a categorical summary will be presented for the 12-lead assessments, as well as for the Holter/telemetry 5-lead assessments.

Descriptive statistics will be provided for the following parameters:

- 12-lead
  - Heart Rate (beats/min)
  - PR Interval (msec)
  - QRS Interval (msec)
  - QT Interval (msec)
  - QTc Interval (msec) (correction type not provided in data)
  - QTcB Interval (msec)
  - QTcF Interval (msec)
  - RR Interval (msec)
  - P-Axis (%)
  - R-Axis (%)
  - T-Axis (%)
- Holter/telemetry 5-lead
  - Heart Rate (beats/min)

Verrica Pharmaceuticals Inc.  
Protocol: VP-315-201

Statistical Analysis Plan  
6-Sep-2024

- PR Interval (msec)
- QRS Interval (msec)
- QT Interval (msec)

The number and percentage of subjects will be provided for the following parameters:

- 12-lead
  - Modality (HeartCor, Locally)
  - Overall Assessment/Interpretation (Normal, Abnormal NCS, Abnormal CS)
  - Predominant Rhythm (Normal Sinus Rhythm, Sinus Tachycardia, Sinus Bradycardia, and possibly others)
  - Principal Investigator/Medical Doctor Notification (Yes, No)
- Holter/telemetry 5-lead
  - Predominant Rhythm (Normal Sinus Rhythm, Sinus Tachycardia, Sinus Bradycardia, and possibly others)

The Holter/telemetry 5-lead is to be monitored continuously on injection visits, with a planned start 15 minutes prior to injection and a planned continuance until after the last injection of the day. As a continuous full-length reading, there are no 5-lead baseline or pre-injection values, but the 5-lead full-length reading is to be broken where possible into sub-readings/timepoints (Holter Start, Holter Pre-injection, Holter 5 Minute Post-injection 1, Holter 15 Minute Post-injection 1, Holter 5 Minute Post-injection 2, Holter 15 Minute Post-injection 2, Holter End, and any change in BP occurring during the full-length Holter reading that would qualify as a DLT/TRAESI (these specific changes in BP will be referred to as BP Dips below)).

Due to different sources for recorded times related to the Holter/telemetry 5-lead data, the possibility of mis-ordering timepoints based on recorded times exists; therefore, the sub-readings/timepoint labels of Holter Start and Pre-injection will be considered when determining the Baseline and Pre-injection values as follows.

The 5-lead Baseline value for use in Change from Baseline calculations will be the most recent non-missing value from the following possibilities:

- Holter Start Timepoint on Day of First Treatment Injection

- Holter Pre-injection Timepoint on Day of First Treatment Injection
- BP Dip(s) on Day of First Treatment Injection where Time of Dip(s) < Time of First Treatment Injection, and there are Holter/telemetry 5-lead data associated with these BP Dip(s)

Each subject has his or her own Baseline value per parameter, if determinable, to be used for calculating Change from Baseline.

The 5-lead Pre-injection values for use in Change from Pre-injection for Post-injection Readings on that Same Visit calculations will be the most recent non-missing values, on the Same Visit, from the following possibilities:

- Holter Start Timepoint on Day of Treatment Injection
- Holter Pre-injection Timepoint on Day of Treatment Injection
- BP Dip(s) on Day of Treatment Injection where Time of Dip(s) < Time of Treatment Injection, and there are Holter/telemetry 5-lead data associated with these BP Dip(s)

Each subject has his or her own Pre-injection value per parameter per injection visit, if determinable, to be used for calculating Change from Pre-injection for Post-injection Readings on that Same Visit.

Summaries will present scheduled visit and include baseline (Screening, W1D1, Baseline, W1D2, W1D3, W1 Safety Assessment, W2D1, W2D2, W2D3, W2 Safety Assessment, EOT – not all ECG parameters are collected at all scheduled visits) within the parameters mentioned previously in this section of the SAP and, for continuous parameters, include descriptive statistics for baseline and change from baseline for post-baseline visits, if possible.

Holter/telemetry 5-lead values will also be displayed by predetermined timepoint within scheduled visit and include descriptive statistics for change from pre-injection for post-injection readings on that same visit, if possible. Due to sparsity, the sub-reading/timepoints for any change in BP that would qualify as a DLT/TRAESI will not be included in the summary but will be displayed in the 5-lead listings.

A separate listing will be provided for the continuous parameters from the 12-lead assessment using the safety population, and this listing will include Visit, Recording Date and Time, Heart Rate, Interval and Axis readings, and Change from Baseline.

Verrica Pharmaceuticals Inc.  
Protocol: VP-315-201

Statistical Analysis Plan  
6-Sep-2024

A separate listing will also be provided for the categorical parameters from the 12-lead assessment using the safety population, and this listing will include whether the Assessment was Performed (Yes, No), Visit, Recording Date and Time, the categorical ECG parameters described above, and Abnormal Findings.

Additionally, a separate listing will also be provided for the continuous parameters from the Holter/telemetry 5-lead assessment using the safety population, and this listing will include Visit, Date of Visit, Timepoint, Time of Timepoint, Heart Rate, Interval readings, Change from Baseline, and Change from Pre-injection.

A separate listing will also be provided for the categorical parameter(s) from the Holter/telemetry 5-lead assessment using the safety population, and this listing will include Visit, Date of Visit, Timepoint, Time of Timepoint, and the categorical ECG parameter described above.

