# 2.2.2 Nonclinical Toxicology and Safety

LTX-315 was designed to be administered to tumors accessible for injection in the clinic. A cyclical regimen was used to cover repeat dosing. Although no observable adverse effect levels (NOAELs) could be determined due to the pharmacological action of the compound, these studies generated data that assisted in the selection of a tolerable clinical starting dose.

Based on observations in rats and dogs, an acute reduction in mean arterial pressure was observed after intravenous (IV) administration and likely resulted from vasodilation in peripheral circulation with a decrease in total vascular resistance and was not considered to be a direct cardiac effect. In vitro studies evidenced that this transient hemodynamic effect may be caused by interaction between LTX-315 and the MRGX2 receptor on mast cells affecting peripheral blood pressure (BP) by histamine release.

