- c. Vital signs (e.g., temperature, HR, BP) will be obtained at screening and at each treatment prior to application of study drug. Height and weight will be collected at Screening and EOS. Subjects must be supine for at least 5 minutes before BP and pulse rate measurements. On VP-315 dosing days, BP will be monitored serially just prior to injection, at 1, 3, and 5 minutes after each injection, and then every 5 minutes until 2 hours post last injection of the day using a manual/automated cuff system. For subjects in Part 2 (Cohorts 4 and 5 expansion groups), monitoring of BP has been decreased to 1-hour by the SRC following their safety meetings. An additional hour may be continued at the discretion of the PI.
- d. Fitzpatrick Skin Type and lesion count.
- e. Limited physical examination (dermatological exam). Symptom- or AE-directed physical examination may be performed if warranted. (See Source/CRF for further outline of assessment.)
- f. Resting 12-lead ECGs (equipment provided by ECG Core Lab) will be recorded after the subject has been supine and at rest for at least 5 minutes at all visits, and prior to dosing on VP-315 dosing days. On VP-315 dosing days, 5-electrode Holter/telemetry (equipment provided by ECG Core Lab) will also be monitored continuously starting 15 minutes prior to injection and continuing 2-hours post last injection of the day. For subjects in Part 2 (Cohorts 4 and 5 expansion groups), Holter/telemetry monitoring has been decreased to 1-hour by the SRC following their safety meetings. An additional hour may be continued at the discretion of the PI. Note, in the event of EGC Core Lab equipment failure for the 12-lead ECG, sites may use their own 12-lead ECG machine and contact the ECG Core Lab for directions regarding upload to the study portal.
- g. Clinical laboratory assessments to include a complete blood count and chemistry panel; samples will be collected at Screening, the Safety Assessment Visit, Unscheduled Visit and at the EOS (for subjects with excised lesions on both the face and the body, clinical laboratory samples will be collected only at the second EOS visit (i.e., at the EOS for Body; 2 weeks after excision). Local laboratory procedures and analysis should be used for these tests.

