# 11.5.2 Safety Analyses

All subjects who receive any amount of study drug will be included in the safety analysis. Safety will be evaluated by study part.

All AEs will be coded using the MedDRA dictionary. Tabular summaries of AEs will only consider treatment-emergent adverse events (TEAEs), which are defined as those AEs with a start date on or after first dose of study drug. The incidence of TEAEs will be summarized by system organ class (SOC), preferred term (PT), relationship to study drug, and severity. Serious TEAEs will be summarized by SOC and PT. TEAEs leading to discontinuation as well as TEAEs identified as dose limiting toxicities will be listed and summarized if sufficient counts of either are reported.

Hematology and serum chemistries will be summarized using conventional summary statistics (mean, standard deviation, median, and range). In addition, a change from baseline will be presented. Standard shift tables will also be prepared presenting toxicity grade vs baseline.

Vital signs and ECG results will be summarized in a descriptive manner by calculating the mean, standard deviation, median, and range in the same manner described for laboratory values. Change from baseline for vital signs and ECG parameters will also be summarized. For ECG parameters, both QTcB (Bazett's correction) and QTcF (Fridericia's correction) will be displayed.

Cutaneous Reaction Assessments will be summarized using counts and percentages for each severity level (none, mild, moderate, severe). Separate summaries will be presented for each cutaneous reaction type and visit.

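### SAP 9.4 reports QT without rate correction at every post-injection Holter timepoint and gives QTcB and QTcF only for 12-lead ECGs taken before dosing or on non-dosing visits

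*SAP*

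**What the plan says.** **12-lead timing.** Protocol Table 8-1, footnote f, has the resting 12-lead ECG recorded "at all visits, and prior to dosing on VP-315 dosing days". The table grid marks it at Screening, treatment days, the Safety Assessment Visit and EOT. No 12-lead ECG is scheduled after an injection on a dosing day.

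**Holter timing.** The same footnote has the Holter "monitored continuously starting 15 minutes prior to injection and continuing 2-hours post last injection of the day". The Cohort 4 and 5 expansion groups have 1 hour instead of 2, with a further hour at the investigator's discretion.

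**Holter timepoints in the analysis.** SAP 9.4 says that the Holter has no natural baseline, "but the 5-lead full-length reading is to be broken where possible into sub-readings/timepoints". The post-injection ones are "Holter 5 Minute Post-injection 1, Holter 15 Minute Post-injection 1, Holter 5 Minute Post-injection 2, Holter 15 Minute Post-injection 2, Holter End", plus any blood-pressure change that would qualify as a DLT or TRAE SI (BP Dips). BP Dips go to the listings only. The other timepoints are summarised with change from pre-injection on the same visit.

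**Parameters.** For 12-lead, SAP 9.4 names heart rate, PR, QRS, QT, QTc of unstated type, QTcB, QTcF, RR and the axes. For Holter it names heart rate, PR, QRS and QT.

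**Protocol commitment.** Protocol 11.5.2 states: "For ECG parameters, both QTcB (Bazett's correction) and QTcF (Fridericia's correction) will be displayed". It names no device. Protocol 11.1 says the SAP will identify where its methods depart from the protocol. SAP 14, which lists those departures, does not mention Holter QTc.

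**The concern.** Uncorrected QT shortens as heart rate rises and lengthens as it falls. A change in QT can be read as a repolarisation effect only if heart rate is stable or the interval is corrected for it. The plan corrects QT where heart rate has least reason to have been disturbed by a recent injection, and leaves it uncorrected where disturbance is most plausible.

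Protocol 2.2.2 reports an acute fall in arterial pressure in animals after intravenous dosing, which "likely resulted from vasodilation in peripheral circulation with a decrease in total vascular resistance". The same sentence adds that this was not considered a direct effect on the heart. A heart-rate change shortly after injection is therefore plausible, although the documents do not quantify one.

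At stake is the reading of two safety displays. The Holter table could show little change in QT when corrected QT has lengthened, or an apparent shortening or lengthening that is only a rate effect. The 12-lead QTc tables could be taken as evidence about the hours after injection, which they do not cover.

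**Working it through.** **Step 1: which ECG readings fall within hours after an injection?**

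| Source | Scheduled times | Corrected QT planned? |
|---|---|---|
| 12-lead | Screening; before dosing on dosing days; Safety Assessment; EOT | Yes: QTcB and QTcF |
| Holter, summarised | 5 and 15 min after injections 1 and 2; Holter End (planned at 2 h after the last injection, 1 h in expansion groups) | No: QT only |
| Holter, listed only | BP Dips | No: QT only |

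Every scheduled reading within hours after injection is in the last two rows, and none carries a corrected QT.

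**Step 2: is the information lost?** No. SAP 9.4 summarises Holter heart rate and QT at the same timepoints, and its continuous-parameter listing gives heart rate and the interval readings by subject and timepoint. With RR = 60/HR in seconds:

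- QTcF = QT / RR^(1/3)
- QTcB = QT / RR^(1/2)

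Example: QT 366.9 ms at 90 bpm gives QTcF = 366.9 / (60/90)^(1/3) = 420 ms. A heart-rate rounding error of 0.5 bpm moves this by about 0.8 ms.

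**Step 3: how large could the rate effect be?** The plan gives no QTc figure to reproduce and no heart-rate change, so the inputs below are assumptions: resting heart rate 65 bpm and QT 400 ms.

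At rest, QTcF = 400 / (60/65)^(1/3) = 410.8 ms.

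| Heart rate after injection | QTcF if QT stays at 400 ms | Change in QT shown | Change in QTcF | QT if QTcF stays at 410.8 ms | Change in QT shown |
|---|---|---|---|---|---|
| 75 bpm | 430.9 ms | 0 ms | +20 ms | 381.4 ms | -19 ms |
| 85 bpm | 449.2 ms | 0 ms | +38 ms | 365.8 ms | -34 ms |

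**Step 4: does it depend on the starting values?** Take instead 70 bpm and QTcF 400 ms, again assumed.

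- With QTcF constant, a rise to 75, 80 or 90 bpm shifts QT by -8.6, -16.5 or -30.5 ms. A fall to 60 bpm shifts it by +20.0 ms.
- With a true QTcF increase of 20 ms, the planned table would show +9.9 ms at 75 bpm, +1.6 ms at 80 bpm and -13.1 ms at 90 bpm.

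Under these inputs a 10 bpm rise nearly hides a 20 ms prolongation, and a 20 bpm rise reverses its sign.

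**Step 5: does the choice of correction matter?** For the rise from 70 to 80 bpm, holding QTcB rather than QTcF at 400 ms implies a QT shift of -23.9 ms rather than -16.5 ms. The two corrections differ enough that one should be named primary in advance.

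**The case against.** **Heart rate is shown beside QT.** This stands in part. A reader of the continuous Holter summary would see a marked heart-rate rise and could discount the QT figure. A reader might infer that the plan cannot reveal a QTc effect after injection. The documents do not support that, because both inputs are captured and listed. What is missing is the derivation. Mean QT and mean heart rate in separate rows give at best an approximate average, not the spread or the largest individual change in corrected QT.

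**The nonclinical text does not point to the heart.** This also stands. Protocol 2.2.2 and 2.3.1 both describe the hypotension as peripheral and not cardiac. QTc is not among the safety endpoints in Protocol 11.4.1, and the study is descriptive and unpowered. Nothing in the documents suggests a known QT risk, so the gap is in the display of safety data and does not affect an endpoint.

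**The protocol may promise QTc for 12-lead only.** A reader might infer that the SAP breaks Protocol 11.5.2 without saying so. That is arguable. Table 8-1 lists 12-lead ECG and Holter as separate procedures, and SAP 9.4 does display both corrections for 12-lead. Protocol 8.4.3 covers both devices and says the core laboratory will report QTc, without saying from which. The wording is ambiguous and SAP 14 does not settle it.

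**The 12-lead readings may also reflect exposure.** A reader might infer that no drug is acting when they are taken, or that the Holter readings are the only ones with VP-315 in the blood. Neither is documented. No half-life or plasma level is given, and the W1D2 pre-dose 12-lead falls near the 24-hour PK sample. The supportable description is about timing: the Holter readings are the only ones scheduled within hours after injection.

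**Conclusion.** The point holds as a gap in the planned outputs. On the SAP's own parameter lists, no table or listing gives a corrected QT at any post-injection timepoint, although the plan captures everything needed to calculate one.

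The structural finding rests on the text alone. The size rests on assumed heart rates and intervals. In the main illustration, a rise of 10 to 20 bpm corresponds to 20 to 38 ms of QTcF change that the QT table shows as zero, or to an apparent QT shortening of 19 to 34 ms with no change in QTcF. If heart rate barely moves, the distortion is small: under 9 ms for a 5 bpm rise from 70 bpm. The actual change is unknown from the documents.

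The improvement is worth making because it costs little and concerns the only repolarisation data scheduled close to injection.

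**What to change.** In SAP 9.4:

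1. Add QTcF (primary) and QTcB as derived Holter parameters, each calculated from that sub-reading's own QT and heart rate, with RR = 60/HR.
2. Summarise both with change from pre-injection at 5 and 15 minutes after injections 1 and 2 and at Holter End. Add them to the Holter listing at every sub-reading, including BP Dips.
3. Label the 12-lead QTc tables as containing pre-dose and off-dose readings only.
4. State in SAP 14 how Protocol 11.5.2 is read for Holter. If QTc is kept to 12-lead after all, declare that there with the reason.

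The cost is SAP wording and a few lines of programming, with no new data collection. The downside is small: Holter QT is less precise than 12-lead QT, but the SAP already reports it uncorrected. The change should be made before database lock, since SAP 5.2 treats anything added later as post hoc.
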